11.3.5 Other toxicities

If toxicities are \leq grade 2, manage symptomatically if possible and retreat without dose reduction.

If toxicities are \geq grade 3, except for anemia, treatment should be withheld until resolution to \leq grade 1 or baseline if baseline was greater than grade 1, then reinstituted, if medically appropriate, at the next lower dose level.

For any grade 3 or 4 toxicity not mentioned above, treatment should be withheld until the patient recovers completely or to grade 1 toxicity. The treatment should then be resumed at the next dose level. For grade 1 or 2 toxicities, no dose reduction should be made.

A maximum of two weeks will be permitted for resolution of grade 3 or 4 toxicities. If toxicity has not resolved by the end of two weeks, patient will be taken off study.

IRB#: 07-022A(13)

Dose Modification Table

Dose Level	Bicalutamide (mg)	
(starting dose)		
0	150	
-1	100	
-2	50	

11.3 Concomitant Treatment/ Medications for Symptom Relief

Irradiation is permitted during the study for treatment of symptomatic breast pain, as outlined above, if it is deemed feasible and appropriate care. Administration of other chemotherapy, immunotherapy, biologic therapy or anti-tumor hormonal therapy during the study is not allowed. Supportive care, including but not limited to antiemetic medications, may be administered at the discretion of the investigator. Concurrent treatment with bisphosphonates is allowed. All concomitant treatments, including blood and blood products, must be reported on the case report form. Granulocyte stimulating factor and/or erythropoietin may be administered at the discretion of the investigator, consistent with institution guidelines.

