4.3 Intervention

Patients will receive bicalutamide at a dose of 150mg PO daily. Patients will be seen monthly for an assessment by a care provider familiar with the protocol. Clinical assessment and serum studies will be performed per protocol (See Time and Events Schedule, Section 10). Patients may be seen before their scheduled monthly follow-up if they are experiencing any adverse effects or symptoms that may be consistent with progression of disease. Patients will undergo a radiologic extent of disease evaluation (EOD) every 3 months. An EOD may be performed earlier than a 3 month interval if progression of disease is suspected. Response will be evaluated using RECIST criteria as complete response (CR), partial response (PR), stable disease (SD) or progressive disease (PD).

If a patient experiences unacceptable toxicity at the initial dose level, up to two dose reductions of 50mg each will be permitted. Dose reduction of bicalutamide from the initial dose of 150mg PO daily to100mg PO daily will occur for an individual patient if that patient experiences unacceptable toxicity. A second dose reduction of 50mg is acceptable. Toxicities will be graded using the NCI Common Terminology Criteria for Adverse Events (CTCAE) Version 3. Treatment may be delayed no more than 2 weeks to allow recovery from acute toxicity. In the event of a treatment delay exceeding 2 weeks, the patient will be withdrawn from the study.

[figure not shown]
A patient will be withdrawn from the study in the following situations:

- For an unacceptable toxicity, defined as a Grade 3 or 4 non-hematologic toxicity after 2 (50 mg) dose reductions (see Section 11.2.5); or
- For unacceptable toxicity that fails to resolve after a maximum treatment delay of 2 weeks; or
- Progression of disease

Treatment with bicalutamide will continue until one or more of the criteria for withdrawal from study are met. After 6 months of treatment, patients will be considered responders if they achieve a CR, PR or SD by RECIST criteria. At the investigator's discretion, and in the absence of disease progression by RECIST criteria, treatment with bicalutamide may continue beyond 6 months. Study drug is provided by AstraZeneca.

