10.0 EVALUATION DURING TREATMENT/INTERVENTION

Day 0 and every 4 weeks (+/- 5 days), the following clinical and laboratory assessments must be done prior to continuation of treatment with bicalutamide:

- History and physical examination, including:
 - Vital signs
 - ECOG performance status
 - o Weight
 - Concomitant medications
- Laboratory assessments, including: (screening labs can be used as Day 0 labs)
 - CBC with differential and platelet count
 - Comprehensive metabolic panel (Na, K, Cl, CO2, BUN, Creatinine, Ca, Glucose, Total Protein, Albumin, Alkaline Phosphatase, Total Bilirubin, AST and ALT)
- Adverse Event Evaluation (toxicity assessment using the NCI CTC version 3)
- Blood for correlative study of hormonal levels including estradiol, total testosterone, free testosterone, and sex-hormone binding globulin will be performed at baseline, after Cycle #1 and at the end of study. (See further description below)

Every 12 weeks (+/- two weeks), tumor assessments will be performed. Patients with measurable disease will be evaluated for complete response (CR), partial response (PR), stable disease (SD) or progressive disease (PD) using RECIST criteria, using the same modality of imaging performed at baseline. Patients with non-measurable disease will be evaluated for either stable disease or progressive disease. Responders and stable disease patients will continue on study unless they develop unacceptable toxicity. Progressive disease or unacceptable toxicity (after a maximum of two dose reductions) will be the criteria for treatment failure and discontinuation from the study.

Response assessment will include:

- Radiologic scans of disease sites (e.g. CT scan of chest, abdomen and pelvis and PET or bone scan if there are bone lesions identified on pre-study bone imaging)
- Measurement of all target lesions that are followed by physical examination
- Patients achieving a CR or PR must have confirmation of response at least 4 weeks following the initial response determination.
- End-of-Study (EOS) Evaluation: At the time patients are removed from study, laboratory and clinical evaluations to assess adverse events (AEs) will be performed. Serum hormone panel including estradiol, free and total testosterone and serum hormone binding globulin will be collected. Radiologic studies for antitumor response will be repeated if they have not been performed within the previous 28 days.

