11.3.2 Breast Pain/Tenderness

If \geq grade 3 breast pain occurs, that is not controlled with non-opioid pain medications (NSAIDs, Tylenol), bicalutamide should be withheld until resolution to \leq to grade 1, then reinstituted at the next lower dose level. If \geq grade 3 breast pain occurs at a reduced dose level, and is not controlled with non-opioid pain medications, bicalutamide should be withheld until resolution to \leq grade 1, then reinstituted at the next lower dose level. If, after 2 dose reductions (to 50mg PO daily), \geq grade 3 breast pain persists, opioid pain medicine is encouraged. If symptoms persist, patient may be referred to a radiation oncologist (if no breast irradiation to palliate symptoms. If none of these interventions successfully alleviates symptoms, and if \geq grade 3 breast pain persists, then patient will be discontinued from study. Toxicity will be reported, and patient will be evaluated as unable to tolerate bicalutamide. If \leq grade 2 breast pain persists, patient may elect to stop treatment on study, or to continue. If patient chooses to discontinue study treatment, toxicity will be noted; however, this will not constitute unacceptable toxicity for purposes of adverse event reporting.

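### At the lowest dose, Section 4.3 withdraws a patient with persistent severe breast pain, while Section 11.3.2 and the irradiation permission keep her on study; no passage says which governs

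*Combined protocol and SAP*

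**What the plan says.** **Withdrawal rule.** Section 4.3 (Intervention) makes withdrawal mandatory for unacceptable toxicity, "defined as a Grade 3 or 4 non-hematologic toxicity after 2 (50 mg) dose reductions". It names no exception for breast pain. It cites Section 11.2.5, which matches no subsection in the body as numbered. A separate bullet withdraws patients whose unacceptable toxicity does not resolve within a two-week delay.

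**Breast-pain rule.** Section 11.3.2 picks up the same patient: "If, after 2 dose reductions (to 50mg PO daily"), "grade 3 breast pain persists, opioid pain medicine is encouraged. If symptoms persist, patient may be referred to a radiation oncologist". Discontinuation comes only at the end of that sequence: "If none of these interventions successfully alleviates symptoms, and if" the pain is still grade 3 or higher.

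**Irradiation.** Section 11.3 (Concomitant Treatment) refers back to this route: "Irradiation is permitted during the study for treatment of symptomatic breast pain, as outlined above, if it is deemed feasible and appropriate care".

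**Failure rule.** Section 10.0 says that progression or "unacceptable toxicity (after a maximum of two dose reductions) will be the criteria for treatment failure and discontinuation from the study". It gives no toxicity grade.

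**Other toxicities.** For toxicity of grade 3 or higher, anemia excepted, Section 11.3.5 has treatment withheld until recovery, "then reinstituted, if medically appropriate, at the next lower dose level". It takes the patient off study if a grade 3 or 4 toxicity has not resolved within two weeks. Its dose table ends at level -2 (50 mg), and Section 11.3 (Dosing Delays/Dose Modifications) caps reductions at two.

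**Endpoints.** Section 14.0 divides patients with CR, PR or SD after 6 months by all patients treated, with success at 4 or more of 28. It also defines a safety endpoint: the percentage able to tolerate daily treatment for 6 months with at most two reductions.

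**The concern.** A patient at 50 mg with persistent grade 3 breast pain meets the Section 4.3 withdrawal rule at the moment Section 11.3.2 starts offering opioids and then a radiation referral. A site cannot follow both. In a multicenter trial, two sites could treat the same situation differently and each point to a passage in support.

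This reaches the results because the primary rate is taken over all treated patients. A patient withdrawn at, say, month 4 stays in the denominator. Section 10.0 schedules no scan after the end-of-study evaluation, so she would have no 6-month CR, PR or SD. If kept on drug, she could still be one of the 4 successes. Her status in the tolerability endpoint turns on the same choice. Breast pain is the first item in the anticipated toxicities for women in Section 5.1, which is ordered by likelihood, so this is a foreseeable case.

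**Working it through.** **1. The passages side by side, at 50 mg after two reductions**

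| Situation | Section 4.3 | Toxicity-specific section |
|---|---|---|
| Grade 3+ breast pain persists | withdraw | 11.3.2: opioids, possible radiation referral, discontinue only if these fail |
| Grade 3+ hot flashes persist | withdraw | 11.3.3: off study |
| Liver tests remain elevated | withdraw if grade 3 or 4 | 11.3.4: off study |
| Grade 3-4 hematologic (not anemia), unresolved at two weeks | two-week bullet, if classed as unacceptable | 11.3.5: off study |
| Grade 3-4 hematologic (not anemia), resolved within two weeks | first bullet does not apply (non-hematologic only) | 11.3.5: restart at a lower level, but none exists |

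The first row is the conflict and the last is the secondary gap. Section 11.3.2 gives no time limit for trying opioids or radiation, and the two-week limit in Section 11.3.5 is worded for grade 3 or 4 toxicities generally. That adds doubt about how long the breast-pain route may run.

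**2. The plan's own operating characteristics**

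Inputs from Section 14.0: n = 28, success at 4 or more, rates 5% and 20%. With X binomial:

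- Type I error = P(X ≥ 4 | 28, 0.05) = 0.0491; the plan states 5%.
- Power = P(X ≥ 4 | 28, 0.20) = 0.8398, so type II error = 0.1602; the plan states 16%.

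Both reproduce.

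**3. How many patients**

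The documents have no rate for women at this dose. Section 3.2 gives figures for men: breast pain in 73.6% in the early-disease program and, with gynecomastia, 35-40% in the trials against castration. In the first source over 90% of cases were mild to moderate, so under 10% were severe.

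- 0.736 × 0.10 × 28 = 2.06
- 0.35 × 0.10 × 28 = 0.98, and 0.40 × 0.10 × 28 = 1.12

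The second line assumes that the severity split carries over to different trials. Both are upper bounds, since only pain persisting through two reductions counts. A working range is 0 to 2 of 28.

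**4. Effect on the decision rule**

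Compare affected patients who always fail (withdrawn) with affected patients who have the same chance of response as the others (kept):

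| Affected | Handling | Type I error | Power |
|---|---|---|---|
| any number | kept, same chance | 0.0491 | 0.8398 |
| 1 | always failure: P(X ≥ 4 of 27) | 0.0437 | 0.8177 |
| 2 | always failure: P(X ≥ 4 of 26) | 0.0387 | 0.7932 |

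Check for one patient: the verdict changes only if exactly 3 of the other 27 succeed and she would have succeeded too. P(exactly 3 of 27) is 0.1068 at 5% and 0.1105 at 20%. The shifts are 0.05 × 0.1068 = 0.0053 and 0.20 × 0.1105 = 0.0221, about 0.5 and 2.2 percentage points, in agreement with the table.

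**The case against.** The best answer is that the specific section overrides the general one. The table of contents numbers dose modifications as 11.2, so the Section 4.3 reference to 11.2.5 apparently means the current Section 11.3.5, Other toxicities. One sentence there is confined to toxicities not already covered, and breast pain is covered, with its own exit rule. On that reading Section 4.3 summarizes the default and Section 11.3.2 governs breast pain. This is plausible, and it rules out the stronger inference that no patient could ever still be on study to receive irradiation. But no passage states the precedence, and the Section 4.3 bullet is unqualified.

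Three other inferences go too far:

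- *That Section 10.0 makes the grade 3-4 rule the definition of treatment failure.* It refers to unacceptable toxicity without a grade and is compatible with Section 11.3.2. The term needs aligning, but it is not a second contradiction.
- *That no rule can be carried out for neutropenia or thrombocytopenia at 50 mg.* The two-week removal rule in Section 11.3.5 works, and restarting is conditional on medical judgment. Only the event that resolves within two weeks is left without a workable instruction.
- *That the verdict has an 11% chance of turning on this.* The 10.7% and 11.1% figures presuppose an affected patient who would otherwise be a success.

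Timing also limits the effect. Section 3.2 says that breast symptoms typically developed over the first 6 to 9 months, so some cases would come too late to affect the 6-month endpoint.

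**Conclusion.** The point holds as a contradiction in exit instructions with a small expected numerical effect. Section 4.3 read as written and Section 11.3.2 with the irradiation permission cannot both be followed for severe breast pain at 50 mg. The likely intent can be guessed but is not stated.

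For one affected patient, counting her always as a failure costs about 0.5 points of type I error (0.049 to 0.044) and 2.2 points of power (0.840 to 0.818). This rests on four assumptions: such a patient exists (0 to 2 of 28, from data in men); the event precedes the 6-month assessment; if kept, she has the same chance of response as the others; and withdrawal for toxicity counts as non-response. The last is inferred from the all-treated denominator, because Section 14.0 has no explicit rule for withdrawal due to toxicity. The tolerability endpoint is exposed to the same ambiguity. The hematologic restart gap is secondary and narrow.

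**What to change.** Reconcile Sections 4.3, 11.3.2, 11.3.5 and the concomitant-treatment section so that one exit rule applies at dose level -2:

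- State whether Section 4.3 or Section 11.3.2 governs breast pain, and make the irradiation permission agree.
- Correct the cross-reference to 11.2.5 in Section 4.3.
- Say how the two-week limit relates to the breast-pain steps.
- Make the restart wording in Section 11.3.5 workable for a patient already at level -2, and reconcile its scope (all but anemia) with that of Section 4.3 (non-hematologic).
- Use the term unacceptable toxicity in Section 10.0 in the same sense as elsewhere.
- List patients affected at level -2 beside the primary result, with the timing of the event and how each was counted.

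The clinical rule is for the investigators to choose; none is proposed here. The cost is wording in five places and one listing, with no extra patients, visits or procedures.

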12.1 CRITERIA FOR THERAPEUTIC RESPONSE/OUTCOME ASSESSMENT

Efficacy, defined as the response rate (CR, PR or SD by RECIST criteria) is the primary endpoint of this trial, and patients with measurable disease will be assessed by standard criteria. Patients with non-measurable disease will be evaluated for SD or progressive disease only. For the purposes of this study, patients should be evaluated radiographically every 12 weeks. In addition to a baseline scan, confirmatory CT scan will also be obtained at least 4 weeks following initial documentation of an objective response.

A radiologist will review all of the scans with non-measurable and measurable sites of disease (e.g. CT scans). Target lesions will be identified prospectively, and recorded on a data collection form. These lesions will be followed over the duration of the study as discussed below. The use of a designated study radiologist and data collection forms should ensure quality assurance and verification of tumor response. At participating sites, staff radiologists may evaluate study scans and the principal investigator will calculate response for prespecified target lesions.

12.2 Definitions

Response and progression will be evaluated in this study using the international criteria proposed by the Response Evaluation Criteria in Solid Tumors (RECIST) Committee [*JNCI* 92(3):205-216, 2000]. Changes in only the largest diameter (uni dimensional measurement) of the tumor lesions are used in the RECIST criteria.

IRB#: 07-022A(13)

Note: Lesions are either measurable or non-measurable using the criteria provided below. The term "evaluable" in reference to measurability will not be used because it does not provide additional meaning or accuracy.

Measurable Disease: Measurable lesions are defined as those that can be accurately measured in at least one dimension (longest diameter to be recorded) as >20 mm with conventional techniques (CT, MRI, x-ray) or as >10 mm with spiral CT scan. All tumor measurements must be recorded in millimeters (or decimal fractions of centimeters).

Non-measurable Disease: All other lesions (or sites of disease), including small lesions (longest diameter <20 mm with conventional techniques or <10 mm using spiral CT scan), are considered non-measurable disease. Bone lesions, leptomeningeal disease, ascites, pleural/pericardial effusions, lymphangitis cutis/pulmonis, inflammatory breast disease, abdominal masses (not followed by CT or MRI), and cystic lesions are all non-measurable.

Target Lesions: All measurable lesions up to a maximum of five lesions per organ and 10 lesions in total representative of all involved organs should be identified as target lesions and recorded and measured at baseline. Target lesions should be selected on the basis of their size (lesions with the longest diameter) and their suitability for accurate repeated measurements (either by imaging techniques or clinically). A sum of the longest diameter (LD) for all target lesions will be calculated and reported as the baseline sum LD. The baseline sum LD will be used as reference by which to characterize the objective tumor response.

Non-target Lesions: All other lesions (or sites of disease) should be identified as non-target lesions and should also be recorded at baseline. Non-target lesions include measurable lesions that exceed the maximum numbers per organ or total of all involved organs as well as non-measurable lesions. Measurements of these lesions are not required but the presence or absence of each should be noted throughout followup.

12.3 Guidelines for Evaluation of Measurable Disease

All measurements should be taken and recorded in metric notation using a ruler or calipers. All baseline evaluations should be performed as closely as possible to the beginning of treatment and never more than 4 weeks before the beginning of the treatment.

Tumor lesions that are situated in a previously irradiated area are considered measurable if there is clear disease progression following radiation therapy. The same method of assessment and the same technique should be used to characterize each identified and reported lesion at baseline and during follow-up. Imaging-based evaluation is preferred to evaluation by clinical examination when both methods have been used to assess the antitumor effect of a treatment.

IRB#: 07-022A(13)

Clinical Lesions: Clinical lesions will only be considered measurable when they are superficial (e.g., skin nodules and palpable lymph nodes). In the case of skin lesions, documentation by color photography, including a ruler to estimate the size of the lesion, is recommended.

Chest X-ray: Lesions on chest x-ray are acceptable as measurable lesions when they are clearly defined and surrounded by aerated lung. However, CT is preferable.

Conventional CT and MRI: These techniques should be performed with cuts of 10 mm or less in slice thickness contiguously. Spiral CT should be performed using a 5 mm contiguous reconstruction algorithm. This applies to tumors of the chest, abdomen, and pelvis. Head and neck tumors and those of extremities usually require specific protocols.

Ultrasound (US): When the primary endpoint of the study is objective response evaluation, US should not be used to measure tumor lesions. It is, however, a possible alternative to clinical measurements of superficial palpable lymph nodes, subcutaneous lesions, and thyroid nodules. US might also be useful to confirm the complete disappearance of superficial lesions usually assessed by clinical examination.

Endoscopy, Laparoscopy: The utilization of these techniques for objective tumor evaluation has not yet been fully and widely validated. Their uses in this specific context require sophisticated equipment and a high level of expertise that may only be available in some centers. Therefore, the utilization of such techniques for objective tumor response should be restricted to validation purposes in reference centers. However, such techniques can be useful to confirm complete pathological response when biopsies are obtained.

Tumor Markers: Tumor markers alone cannot be used to assess response. If markers are initially above the upper normal limit, they must normalize for a patient to be considered in complete clinical response.

Cytology, Histology. These techniques can be used to differentiate between partial responses (PR) and complete responses (CR) in rare cases (e.g., residual lesions in tumor types such as germ cell tumors, where known residual benign tumors can remain).

The cytological confirmation of the neoplastic origin of any effusion that appears or worsens during treatment when the measurable tumor has met criteria for response or stable disease is mandatory to differentiate between response or stable disease (an effusion may be a side effect of the treatment) and progressive disease.

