6.1 CRITERIA FOR SUBJECT ELIGIBILITY

6.2 Subject Inclusion Criteria

A patient will be eligible for androgen receptor expression testing if the following criteria are met:

- Pathologically confirmed adenocarcinoma of the breast which is ER(-) and PR(-).
- Non-measurable or Measurable, metastatic disease

IRB#: 07-022A(13)

A patient will be eligible for participation in the therapeutic trial if the following criteria are met:

- Androgen receptor expression testing confirms that the patient's tumor is ER(-)/PR(-) /AR(+). ER, PR and AR are considered positive if greater than 10% of cell nuclei are immunoreactive. Receptor testing may be performed on either primary tumor specimen or tissue from a metastatic site.
- Prior neo-adjuvant or adjuvant chemotherapy is allowed. Any number of chemotherapy regimens are allowed for metastatic disease. There is no restriction on prior treatment with hormonal agents.
- Prior treatment with trastuzumab must have been given if patient has Her2/neu positive disease (defined as IHC=3+ or FISH amplified).
- At least 2 weeks since prior cytotoxic chemotherapy. Patients should have recovered from all acute effects of such therapy.
- Absence of active brain metastatic disease or leptomeningeal disease. If patient has a history of brain metastases, lesions must be stable for at least 3 months (as documented by either head CT or brain MRI).
- At least 4 weeks from major surgery with full recovery
- ECOG performance status 0-1
- Age 18 years or greater
- Laboratory parameters as follows:
 - \circ ANC $\geq 1.5 \times 10^9$ cells/L
 - \circ Platelets $\geq 100 \text{ x } 10^9 \text{ cells/L}$
 - $\circ \quad Hgb \geq 9g/dL$
 - AST (SGOT), ALT (SGPT) ≤ 2.5 x upper limit of normal range (ULN); total bilirubin ≤ 1.5 x ULN; alkaline phosphatase ≤ 2.5 x ULN (unless bone metastases are present in the absence of liver metastases), creatinine ≤ 1.5 mg/dL
- If female of childbearing potential, pregnancy test is negative
- If fertile, the patient agrees to use an effective method to avoid pregnancy for the duration of the study
- Informed consent has been obtained

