In some circumstances, it may be difficult to distinguish residual disease from normal tissue. When the evaluation of complete response depends on this determination, it is recommended that the residual lesion be investigated (fine needle aspirate/biopsy) before confirming the complete response status.

Non-measurable disease: Patients with non-measurable disease (ie, bone only disease) will be evaluated only as either stable disease or progressive disease.

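### Eligibility puts no condition on prior radiotherapy, so a patient whose only disease was irradiated before Day 0 can count as a 6-month success through stable disease

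*Combined protocol and SAP*

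**What the plan says.** **Entry.** Section 6.2 accepts "Non-measurable or Measurable, metastatic disease". It sets a chemotherapy interval ("At least 2 weeks since prior cytotoxic chemotherapy") and 4 weeks from major surgery. Section 6.3 sets 3 weeks for investigational drugs. Neither section mentions prior radiotherapy, and neither requires a lesion outside an irradiated field or progression after irradiation.

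**Irradiated lesions.** Section 12.3 says: "Tumor lesions that are situated in a previously irradiated area are considered measurable if there is clear disease progression following radiation therapy". It does not say what happens to an irradiated lesion that has not progressed. Section 12.2 has two classes only ("Lesions are either measurable or non-measurable using the criteria provided below"), and the non-measurable class takes in "All other lesions (or sites of disease), including small lesions".

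**Scoring.** Section 12.1 states: "Patients with non-measurable disease will be evaluated for SD or progressive disease only". Section 12.4 repeats this, with bone-only disease as its example: "Patients with non-measurable disease (ie, bone only disease) will be evaluated only as either stable disease or progressive disease". Under 12.4 a persisting non-target lesion is SD. A new lesion, or unequivocal progression of an existing non-target lesion, is progressive disease.

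**Decision.** Section 14.0 counts CR, PR or SD at 6 months as success, divides by all patients treated, and calls the drug worth further study at 4 or more successes in 28. It states a type I error of 5% at a true rate of 5%, and a type II error of 16% at 20%.

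**The concern.** The trial has no control arm, and SD counts as much as a response. Anything other than the drug that keeps disease stable for 6 months therefore adds directly to the success count. Radiotherapy shortly before Day 0 is one such influence. The plan recognises it in part: 12.3 limits when an irradiated lesion is measurable, and 13.0 removes a patient whose indicator lesion is irradiated during the trial. Neither rule covers a patient who enters with only disease that has already been irradiated.

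Requiring progression at some point before entry would not close this route, because the irradiation could follow that progression. With a cut-off of 4, one such success is a quarter of the evidence needed to recommend further study.

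**Working it through.** **Step 1: follow the route through the text.**

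1. A patient's only metastatic disease is irradiated shortly before Day 0. Nothing in 6.2 or 6.3 excludes this patient.
2. If the lesion is read as non-measurable (12.2 with 12.3), it is a non-target lesion, for which 12.2 says "Measurements of these lesions are not required but the presence or absence of each should be noted throughout followup". Persistence is SD.
3. If it is read as still measurable, it can be a target lesion. Without enough shrinkage for PR or enough growth for progression it is again SD.
4. If it is a bone lesion, 12.2 makes it non-measurable whether irradiated or not, so the sentence in 12.3 never applies. Persistence is SD.
5. In every case 14.0 counts the patient at 6 months, provided no new lesion has appeared.

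The classification in 12.3 therefore does not decide the outcome. The gap is the missing entry condition in 6.2, together with SD counting as success.

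**Step 2: reproduce the plan's figures.** The inputs from 14.0 are n = 28, cut-off 4, rates 5% and 20%. With X the number of successes:

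- P(X ≥ 4), X ~ Bin(28, 0.05) = 0.0491, stated as 5%.
- P(X ≥ 4), X ~ Bin(28, 0.20) = 0.8398, so the type II error is 0.1602, stated as 16%.

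Both agree.

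**Step 3: size of the effect.** Assumption, not in the documents: k of the 28 patients have only irradiated disease and a chance q of being progression-free at 6 months without any drug effect. The other 28 − k succeed at 5%. Then

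P(pass) = P(A + B ≥ 4), with A ~ Bin(k, q) and B ~ Bin(28 − k, 0.05) independent.

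For k = 1 this is (1 − q) × P(B ≥ 4) + q × P(B ≥ 3), with B ~ Bin(27, 0.05), P(B ≥ 4) = 0.0437 and P(B ≥ 3) = 0.1505. At q = 0.5: 0.5 × 0.0437 + 0.5 × 0.1505 = 0.0971.

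| q | k = 0 | k = 1 | k = 2 |
|---|---|---|---|
| 0.1 | 4.9% | 5.4% | 6.0% |
| 0.2 | 4.9% | 6.5% | 8.4% |
| 0.3 | 4.9% | 7.6% | 11.1% |
| 0.5 | 4.9% | 9.7% | 17.3% |
| 0.7 | 4.9% | 11.8% | 24.6% |

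**Step 4: what leaving such patients out does.** If k patients are dropped and not replaced, with the cut-off still 4, type I error and power are 4.4% and 81.8% for k = 1 (n = 27), and 3.9% and 79.3% for k = 2 (n = 26). If such patients never enter and 28 others do, 4.9% and 84.0% are kept.

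**The case against.** **The patient must be stable everywhere, not only in the field.** Any new lesion is progression, and imaging is repeated every 12 weeks in a disease that section 3.1 describes as generally more aggressive than hormone receptor-positive disease. This stands. It means q is freedom from progression for the whole patient, and values such as 0.1 or 0.2 may be nearer the mark than 0.5 or 0.7. That is why the table starts at 0.1.

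**The 5% error is defined at a true rate of 5%.** With k = 1 and q = 0.5 the average rate is (0.5 + 27 × 0.05)/28 = 6.6%, which is above that null. A reader might infer from the table that the stated type I error is wrong. The documents do not support that: the error reproduces at its own null, k is unknown and may be 0. The table shows how much easier passing becomes with no drug effect in the affected patients.

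**A reader might also infer that 12.3 itself creates the problem** by moving non-progressed irradiated lesions into the non-measurable class. That is an inference. The sentence gives a sufficient condition for measurability and is silent on the other case. Since SD counts in either class, this reading is not needed for the point.

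**Safeguards exist.** Section 14.0 reports the measurable-disease rate separately. Section 16.1.2 (Response Review) makes responses subject to central review. Section 1.3 describes entry when the physician judges that therapy must change, which makes a patient with only controlled, irradiated disease less likely. These lower the likely frequency or help interpretation. None changes the count against 4 of 28: the rule uses all treated patients, a stable irradiated lesion is correctly SD on review, and the wording in 1.3 is not an eligibility criterion and does not require progression after radiotherapy.

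**Conclusion.** The point holds as a gap in eligibility and scoring. The text lets a patient whose only disease was irradiated before Day 0 count as a primary-endpoint success through SD, whichever way the lesion is classed, and no other section closes the route.

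Its size rests wholly on assumed k and q. At low q the effect is small: 5.4% to 6.5% for one patient and 6.0% to 8.4% for two, at q = 0.1 to 0.2. At q = 0.7 it reaches 11.8% and 24.6%. The route is plain from the text, but its frequency is unknown. This is a cheap improvement that removes a possible bias from a small count, not an error in the stated design.

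**What to change.** 1. State in 6.2 and 12.3 that disease lying wholly within previously irradiated fields, and not progressed since irradiation, cannot be a patient's only disease and cannot by itself support SD for the primary endpoint. This covers bone lesions and lesions large enough to measure, so it does not depend on how 12.3 is read.
2. Record the field and end date of prior radiotherapy. History of prior therapy is already collected under 8.1, and the submission chart in 16.1.3 already has a Past Treatment Form, so this is a small addition.
3. For patients already entered, identify those with only such lesions from baseline data alone. Report the primary rate and the 4-of-28 result with and without them, giving the reduced denominator. The separate measurable-disease rate in 14.0 does not replace this.

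**Cost.** A sentence or two in each section, a small addition to an existing form, and one extra line in the results. A few patients become ineligible and accrual is slightly slower. If already-entered patients are left out and not replaced, power falls from 84.0% to 81.8% for one patient or 79.3% for two.
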